3 OVERALL STUDY DESIGN

3.1 Study Design

The study will be conducted in compliance with the International Council for Harmonisation (ICH) of Technical Requirements for Registration of Pharmaceuticals for Human Use/Good Clinical Practice (GCP) and applicable regulatory requirements.

This is an interventional active-controlled, open-label, randomized Phase 3 study to compare the efficacy and safety of luspatercept (ACE-536) versus epoetin alfa for the treatment of anemia due to IPSS-R very low, low or intermediate risk MDS in ESA naïve subjects who require RBC transfusions.

The study is divided into the Screening Period, a Treatment Period and a Post-treatment Follow-up Period. See [Figure 2](#) for more details and refer to [Section 6](#) for a full list of study procedures/assessments.

Screening Period

Upon giving written informed consent, subjects enter the Screening Period to determine eligibility. Subject screening procedures are to take place within 35 days prior to randomization. During the Screening Period, the subject will undergo safety and other assessments to determine eligibility for the randomized study.

Central review of bone marrow aspirate smear, peripheral blood smear and cytogenetics will be used to confirm MDS diagnosis according to the WHO 2016 classification ([APPENDIX B](#)) and to determine the baseline IPSS-R risk classification ([Greenberg, 2012](#)). A bone marrow biopsy will be collected only when adequate aspirate is not attainable.

Transfusion history must be available for at least 16 weeks immediately preceding and including the date of randomization. Refer to [Table 3](#) for a full list of study procedures/assessments.

The sponsor may review key eligibility criteria as well as relevant data (eg, central laboratory reports and cytomorphology/cytogenetic reports) and communicate as necessary with the investigator prior to randomization of a subject.

Randomization

Approximately 350 eligible subjects will be randomized by a central randomization procedure using integrated response technology (IRT) at a 1:1 ratio to one of the below treatment arms:

- **Experimental Arm:** luspatercept (ACE-536): starting dose of 1.0 mg/kg subcutaneous injection every 3 weeks (21 days; Q3W). Dose levels can be increased in a stepwise manner beyond the starting dose to 1.33 mg/kg, and up to a maximum of 1.75 mg/kg. See [Section 7.2.1](#) for details.
- **Control Arm:** epoetin alfa (EPREX[®]/ERYPO[®] or PROCRI[®]): starting dose of 450 IU/kg (maximum total starting dose is 40,000 IU) subcutaneous injection once every week (7 days; QW). Dose levels can be increased in a stepwise manner beyond the starting dose to 787.5 IU/kg, and up to a maximum of 1,050 IU/kg (with a maximum

total dose of 80,000 IU). Individual epoetin alfa doses according to body weight will be rounded as described in [Section 7.2.2](#) in more detail.

Randomization will be stratified based on the following factors:

- RBC transfusion burden at baseline
 - < 4 pRBC units/ 8 weeks
 - ≥ 4 pRBC units/ 8 weeks
- Ring sideroblast (RS) status at baseline (with RS+ defined as Ring sideroblast ≥ 15% of erythroid precursors in bone marrow or ≥ 5% (but < 15%) if SF3B1 mutation is present).
 - RS+
 - RS-
- Endogenous Serum Erythropoietin (sEPO) level at baseline.
 - ≤ 200 U/L
 - > 200 U/L

Crossover between treatment arms is not permitted during the Study Treatment Period.

Treatment Period

The first dose of investigational product (IP) should be administered on the same day after randomization, but at the latest within 3 days of randomization. More details will be provided in the IRT manual for additional information on randomization utilizing IRT.

Subjects on the luspatercept arm will receive IP every 3 weeks (21 days) (ie, at the Week 1 Day 1 (W1D1) Visit, W4D1 Visit; W7D1 Visit, etc.).

Subjects on the epoetin alfa arm will receive IP every week (7 days) (ie, at the W1D1 Visit, W2D1 Visit; W3D1 Visit, etc.).

Details on IP administration and intra-individual dose titration are outlined in [Section 7](#).

In both treatment arms, best supportive care (BSC) may be used in combination with study treatment when clinically indicated per investigator. Best supportive care includes, but is not limited to, treatment with transfusions, antibiotic, antiviral and/or antifungal therapy, and nutritional support as needed. Best supportive care for this study excludes the use of ESAs outside of the study treatment. Please refer to [Section 8](#) for more details on permitted and prohibited concomitant medications and procedures.

Subjects should receive IP through to a minimum of the 24-Week MDS Disease Assessment Visit scheduled for Day 169, unless the subject experiences unacceptable toxicities, withdraws consent, or meets any other treatment discontinuation criteria.

The MDS Disease Assessment ([Section 6.4.2](#)) performed on Day 169 (and every 24 weeks thereafter [ie, Day 337, Day 505, etc.]); [Section 6.4.2](#)) consists of the investigator's assessment of clinical benefit from IP and status of underlying disease. For subjects to remain on treatment beyond this timepoint both of the following criteria must be confirmed:

- Evidence of clinical benefit defined as a transfusion reduction of ≥ 2 pRBC units/8 weeks compared to the baseline (for any consecutive 8-week period within the 12 weeks immediately preceding Day 169 and every 24 weeks thereafter [ie, Day 337, Day 505, etc.]).
- Absence of disease progression per IWG criteria for altering natural history of MDS (Cheson, 2006) based on central morphological assessment of bone marrow, peripheral blood and cytogenetics results.

Based on the outcome of these assessments, subjects will either be discontinued from treatment with IP and enter the Post-treatment Follow-up Period or continue open-label treatment with their assigned IP as long as the above criteria continue to be met or until the subject experiences unacceptable toxicities, withdraws consent, or meets any other discontinuation criteria.

For subjects to continue open-label treatment with IP, scheduled MDS disease assessments will be repeated at the 48-Week MDS Disease Assessment Visit (ie. Day 337) and every 24 weeks thereafter (see Section 6.4.2 for details) to confirm continued clinical benefit and absence of disease progression as per above criteria.

Serial measurements of safety and efficacy will occur at scheduled study visits as outlined in Table 3. Laboratory analyses will be performed centrally. Local laboratories are allowed in cases when timely results are needed (eg, pre-dose Hgb assessments, study treatment dosing decisions, hematology assessments between clinic visits, adverse event). In these circumstances, a split sample should still be collected and sent to the central laboratory for analysis. Where discrepancies are present, results of the central laboratory will be used to determine response assessments.

An End of Treatment (EOT) Visit evaluation will be performed for subjects who are withdrawn from treatment for any reason as soon as possible after the decision to permanently discontinue treatment has been made (Section 6.2.2).

Post-treatment Follow-up Period

The Post-treatment Follow-up Period consist of the 42-Day Safety Follow-up (Section 6.3.1), which includes (but is not limited to) the collection of adverse events (AEs), concomitant drugs and RBC-transfusion data, and the Long-term Follow-up (Section 6.3.2).

The transfusion data collection will continue until 8 weeks from the date of last dose of IP or from the date of the EOT Visit (whichever is later).

[figure not shown]
In addition, continuation of monitoring for other malignancies/pre-malignancies and progression to AML will occur in the Long-term Post-treatment Follow-up Period along with data collection of subsequent MDS therapies, and overall survival for 5 years from the date of the first dose of IP, or 3 years from the last dose (whichever occurs later), unless the subject withdraws consent from the study, dies or is lost to follow-up. For that purpose, visits (which may consist of telephone contacts from the site) will be conducted every 12 weeks for the first 3 years from the date of last dose of IP and every 6 months thereafter, if applicable.

An antidrug antibodies (ADA) sample(s) may be required in the Post-treatment Follow-up Period for subjects assigned to the luspatercept arm, who terminate the Treatment Period with less than 1-year of ADA monitoring if a subject is ADA positive at the time of treatment discontinuation.

Data Monitoring Committee (DMC)/Steering Committee (SC)

An external, independent DMC comprised of experts in MDS not involved in the ACE-536-MDS-002 study as well as a SC comprised of study investigators and sponsor representatives will be established. For details on composition and roles please refer to [Section 9.10.4](#) and [Section 9.10.5](#), respectively.

Figure 2: Overall Study Design

Abbreviations: AE = adverse event; EOT = End of Treatment; IP = investigational product; MDS = Myelodysplastic syndromes; QW = once every week; Q3W = every 3 weeks; SC = subcutaneous.

¹ Individual epoetin alfa doses according to body weight will be rounded: up to the next 2,000 IU dose level for Starting Dose Level and Dose Level -1, and up to the next 4,000 IU for Dose Level +1 and Dose Level +2 for doses exceeding a calculated dosing of 56,000 IU according to body weight.

² Crossover between the treatment arms is not permitted during the Study Treatment Period.

3.2 Study Duration for Subjects

The duration of participation for subjects who complete the study will be approximately six years (and may be shorter or longer for individual subjects) consisting of the following phases:

- Screening Period: up to 35 days prior to randomization
- Treatment Period: at least up to the 24-Week MDS Disease Assessment (ie, Day 169) unless the subject experiences unacceptable toxicities, withdraws consent, or meets any other treatment discontinuation criteria (eg, absence of clinical benefit, or disease progression per IWG criteria for altering natural history of MDS ([Cheson, 2006](#)).
- Post-treatment Follow-up Period: 5 years from the date of the first dose of IP, or 3 years from the last dose (whichever occurs later), unless the subject withdraws consent from the study, dies or is lost to follow-up. Long-term Follow-up visits may be conducted as telephone contacts from the site.

3.3 End of Trial

The End of Trial is defined as either the date of the last visit of the last subject to complete the post-treatment follow-up, or the date of receipt of the last data point from the last subject that is required for primary, secondary and/or exploratory analysis, as prespecified in the protocol, whichever is the later date.

The sponsor may end the trial when all key endpoints and objectives of the study have been analyzed and the availability of a roll-over protocol exists into which subjects remaining on study may be consented and continue to receive access to luspatercept and/or complete long-term follow-up. Such a protocol would be written for a compound that would not yet be commercially available.

4 STUDY POPULATION

4.1 Number of Subjects

Approximately 350 subjects with anemia due to IPSS-R very low, low, or intermediate risk MDS who are ESA naïve with endogenous sEPO levels of < 500 U/L and who require RBC transfusions (ie, 2 to 6 pRBC units in the 8 weeks before randomization) will be randomized worldwide.

4.2 Inclusion Criteria

Subjects must satisfy the following criteria to be randomized in the study:

- 1) Subject is ≥ 18 years of age the time of signing the informed consent form (ICF).
- 2) Subject must understand and voluntarily sign an ICF prior to any study-related assessments/procedures being conducted.
- 3) Subject is willing and able to adhere to the study visit schedule and other protocol requirements.
- 4) Subject has a documented diagnosis of MDS according to WHO 2016 classification ([Section 6.1.1](#), [APPENDIX B](#)) that meets IPSS-R classification ([Greenberg, 2012](#)) of very low, low, or intermediate risk disease, and:
 - < 5% blasts in bone marrow.
- 5) Subject has an endogenous serum erythropoietin (sEPO) level of < 500 U/L.
- 6) Subject requires RBC transfusions, as documented by the following criteria ([Section 6.1.2](#)):
 - A transfusion requirement of 2 to 6 pRBCs units/8 weeks confirmed for a minimum of 8 weeks immediately preceding randomization.
 - Hemoglobin levels at the time of or within 7 days prior to administration of a RBC transfusion must have been ≤ 9.0 g/dL (5.6 mmol/L) with symptoms of anemia (or ≤ 7 g/dL [4.3 mmol/L] in the absence of symptoms) in order for the transfusion to be counted towards meeting eligibility criteria. Red blood cell transfusions administered when Hgb levels were > 9.0 g/dL (or > 7 g/dL in the absence of symptoms) and/or RBC transfusions administered for elective surgery, infections or bleeding events will not qualify as a required transfusion for the purpose of meeting eligibility criteria or stratification.
 - The hemoglobin level after the last RBC transfusion prior to randomization must be < 11.0 g/dL (6.8 mmol/L) (centrally or locally analyzed).
- 7) Subject has Eastern Cooperative Oncology Group (ECOG) score of 0, 1, or 2.
- 8) Females of childbearing potential (FCBP), defined as a sexually mature woman who:
 - 1) has achieved menarche at some point, 2) not undergone a hysterectomy or bilateral oophorectomy or 3) has not been naturally postmenopausal (amenorrhea following cancer therapy or amenorrhea due to other medical reasons does not rule out childbearing potential) for at least 24 consecutive months (ie, has had menses at any time in the preceding 24 consecutive months), must:
 - Have two negative pregnancy tests as verified by the investigator prior to starting study therapy (unless the screening pregnancy test was done within 72 hours of WID1).

Refer to [Section 6.1.14](#) for additional details. She must agree to ongoing pregnancy testing during the course of the study, and after end of study treatment.

- Either commit to true abstinence¹ from heterosexual contact (which must be reviewed on a monthly basis and source documented) or agree to use, and be able to comply with, highly effective contraception² without interruption, 5 weeks prior to starting investigational product, during the study therapy (including dose interruptions), and for 12 weeks after discontinuation of study therapy.

9) Male subjects must:

- Practice true abstinence¹(which must be reviewed prior to each IP administration or on a monthly basis [eg, in the event of dose delays]) or agree to use a condom (latex or non-latex, but not made out of natural [animal] membrane) during sexual contact with a pregnant female or a female of childbearing potential while participating in the study, during dose interruptions and for at least 12 weeks following investigational product discontinuation, even if he has undergone a successful vasectomy.

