4.3 Exclusion Criteria

The presence of any of the following will exclude a subject from randomization (with the randomization date defined as the date in which the subject is randomized in IRT):

1) Subject with the any of the following prior treatments:

- Erythropoiesis-stimulating agents (ESAs)
 - Subjects may be randomized at the investigator’s discretion contingent on the fact that the subject received no more than 2 doses of epoetin alfa (prior treatment with darbepoetin not acceptable for entry into the study). The last dose of epoetin alfa must be ≥ 8 weeks from the date of randomization. A blood sample to determine the endogenous sEPO level (central laboratory) for stratification must be taken within 5 days of randomization unless a prior screening sample analyzed by the central laboratory demonstrated an endogenous sEPO level ≤ 500 U/L.
- Granulocyte colony-stimulating factor (G-CSF), granulocyte-macrophage colony-stimulating factor (GM-CSF), within 8 weeks prior to randomization, unless given for treatment of febrile neutropenia
- Disease modifying agents (eg, immune-modulatory drug [IMiDs such as lenalidomide])
 - Except if the subject received ≤ 1 week of treatment with a disease modifying agent ≥ 8 weeks from randomization, at the investigator’s discretion.
- Hypomethylating agents
 - Subjects may be randomized at the investigator’s discretion contingent that the subject received no more than 2 doses of HMA. The last dose must be ≥ 8 weeks from the date of randomization.

¹ True abstinence is acceptable when this is in line with the preferred and usual lifestyle of the subject. [Periodic abstinence (eg, calendar, ovulation, symptothermal, post-ovulation methods) and withdrawal are not acceptable methods of contraception].

² Highly effective contraception is defined in this protocol as the following (information will also appear in the ICF): Hormonal contraception (for example, birth control pills, injection, implant, transdermal patch, vaginal ring); intrauterine device (IUD); tubal ligation (tying your tubes); or a partner with a successful vasectomy.

- Luspatercept (ACE-536) or sotatercept (ACE-011)
 - Immunosuppressive therapy for MDS
 - Hematopoietic cell transplant
- 2) Subject with MDS associated with del(5q) cytogenetic abnormality or MDS unclassifiable (MDS-U) according to WHO 2016 classification.

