- 16) Subject with known human immunodeficiency virus (HIV), known evidence of active infectious Hepatitis B, and/or known evidence of active Hepatitis C. Local laboratory testing confirming HIV, Hepatitis B, and Hepatitis C status should not have been performed beyond 4 weeks prior to the date of ICF signature.
- 17) Subject with history of severe allergic or anaphylactic reactions or hypersensitivity to recombinant proteins or excipients in luspatercept (see Investigator's Brochure).
- 18) Subject with known hypersensitivity to the active substance or to any of the excipients in epoetin alfa.
- 19) Subject with history of pure red cell aplasia (PRCA) and/or antibody against erythropoietin.

- 20) Female subject who is pregnant or breastfeeding.
- 21) Subject has any significant medical condition, laboratory abnormality, psychiatric illness, or is considered vulnerable by local regulations (eg, imprisoned or institutionalized) that would prevent the subject from participating in the study.
- 22) Subject has any condition including the presence of laboratory abnormalities, which places the subject at unacceptable risk if he/she were to participate in the study.
- 23) Subject has any condition or receives concomitant medication that confounds the ability to interpret data from the study.
- 24) Subject has history of active SARS-CoV-2 infection within 4 weeks prior to screening, unless the subject has adequately recovered from COVID symptoms and related complications as per investigator's discretion and following a discussion with the Medical Monitor. Use of a live COVID-19 vaccine is prohibited within 4 weeks prior to randomization.

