APPENDIX B MYELODYSPLASTIC SYNDROMES WORLD HEALTH ORGANIZATION CLASSIFICATION SYSTEM (2016)

Peripheral Blood and BM Findings and Cytogenetics of Myelodysplastic Syndromes (MDS)					
Name	Dysplastic lineages	Cytopenias ^a	Ring sideroblasts as % of marrow erythroid elements	Bone marrow (BM) and peripheral blood (PB) blasts	Cytogenetics by Conventional karyotype analysis
MDS with single lineage dysplasia (MDS-SLD)	1	1 or 2	< 15% / < 5% ^b	BM < 5%, PB < 1%, no Auer rods	Any, unless fulfills all criteria for MDS with isolated del(5q)
MDS with multilineage dysplasia (MDS-MLD)	2 or 3	1-3	< 15% / < 5% ^b	BM < 5%, PB < 1%, no Auer rods	Any, unless fulfills all criteria for MDS with isolated del(5q)
MDS with ring sideroblasts (MDS-RS)					
MDS-RS with single lineage dysplasia (MDS-RS-SLD)	1	1 or 2	≥ 15% / ≥ 5% ^b	BM < 5%, PB < 1%, no Auer rods	Any, unless fulfills all criteria for MDS with isolated del(5q)
MDS-RS with multilineage dysplasia (MDS-RS-MLD)	2 or 3	1-3	≥ 15% / ≥ 5% ^b	BM < 5%, PB < 1%, No Auer rods	Any, unless fulfills all criteria for MDS with isolated del(5q)
MDS with isolated del(5q)	1-3	1-2	None or any	BM < 5%, PB < 1%, no Auer rods	del(5q) alone or with 1 additional abnormality except -7 or del(7q)
MDS with excess blasts (MDSEB)					
MDS-EB-1	0-3	1-3	None or any	BM 5-9% or PB 2-4%, no Auer rods	Any
MDS-EB-2	0-3	1-3	None or any	BM 10-19% or PB 5-19% or Auer rods	Any
MDS, unclassifiable (MDS-U)					
• with 1% blood blasts	1-3	1-3	None or any	BM < 5%, PB=1% ^c , no Auer rods	Any
• with single lineage dysplasia and pancytopenia	1	3	None or any	BM < 5%, PB < 1%, no Auer rods	Any
• based on defining cytogenetic abnormality	0	1-3	<15% ^d	BM < 5%, PB < 1%, no Auer rods	MDS-defining abnormality
Refractory cytopenia of childhood	1-3	1-3	None	BM < 5%, PB < 2%	Any

^a Cytopenias defined as haemoglobin < 10 g/dL, platelet count < 100 x 10⁹/L, and absolute neutrophil count < 1.8 x 10⁹/L; rarely, MDS may present with mild anaemia or thrombocytopenia above these levels. PB monocytes must be < 1 x 10⁹/L.

^b If SF3B1 mutation is present.

^c 1% PB blasts must be recorded on at least two separate occasions.

^d Cases with ≥ 15% ring sideroblasts by definition have significant erythroid dysplasia, and are classified as MDS-RS-SLD.

Sources: Arber DA, Orazi A, Hasserjian R, Thiele J, Borowitz MJ, Le Beau MM, et al. The 2016 revision to the World Health Organization (WHO) classification of myeloid neoplasms and acute leukemia. Blood 2016;127(20):2391-405.

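### Entry limits marrow blasts only, so a subject with 2% or more blood blasts can be randomized while already above the 1% blood-blast stopping threshold

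*Combined protocol and SAP*

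**What the plan says.** **Entry.** Criterion 4 in Section 4.2 asks for a WHO 2016 diagnosis of MDS, an IPSS-R category of very low, low or intermediate, and "< 5% blasts in bone marrow". The Study Population paragraph of the Protocol Summary is likewise confined to marrow. No inclusion or exclusion criterion gives a number for blood blasts.

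**Subtypes.** Appendix B requires blood blasts below 1% for MDS-SLD, MDS-MLD and MDS-RS. It defines the excess-blast subtypes by marrow or blood: EB-1 is "BM 5-9% or PB 2-4%, no Auer rods" and EB-2 is "BM 10-19% or PB 5-19% or Auer rods". Among WHO MDS subtypes, exclusion 2 in Section 4.3 removes only del(5q) disease and "MDS unclassifiable (MDS-U) according to WHO 2016 classification". MDS-U covers blood blasts of 1% recorded on two occasions.

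**On treatment.** Table 5 (luspatercept) and Table 7 (epoetin alfa) carry the same row. Blood blasts of 1% or more on a local or central sample interrupt dosing, and central confirmation on cytomorphology leads to discontinuation. Neither row mentions baseline.

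**Discretion.** At entry, exclusions 21 to 23 are general clauses, and Section 3.1 adds an optional check: "The sponsor may review key eligibility criteria as well as relevant data". On treatment, footnote g allows a centrally read marrow before the decision, footnote h allows contact with the Medical Monitor, and Section 11.1 leaves discontinuation to the treating physician.

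**The concern.** The entry rule and the dosing rule use different blast measures. A subject with marrow below 5% and blood blasts of 2% or more has excess-blast disease under the protocol's own classification table, satisfies the marrow limit, and is above the stopping threshold before the first dose.

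Two things are at stake. The first is safety: Section 1.4.1.1.1 names blood-blast monitoring in the dose rules as a protection against hematologic malignancy, and that protection is weakened if subjects may enter already above the trigger. The second is consistency: the subject can be withdrawn on an unchanged blood picture, and in an open-label trial different sites may handle the same screening result differently.

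**Working it through.** **1. Blood-blast level against each rule (marrow below 5%)**

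| Blood blasts | WHO 2016 class (Appendix B) | Excluded by name at entry? | At or above the stop in Tables 5 and 7? |
|---|---|---|---|
| below 1% | SLD, MLD or RS | no (intended population) | no |
| 1%, recorded twice | MDS-U | yes, exclusion 2 | yes |
| 2-4% | EB-1 | no | yes |
| 5-19% | EB-2 | no | yes |

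The last two rows are the gap.

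**2. Does the IPSS-R limit close it?** Appendix C scores marrow blasts, not blood blasts. Inputs: marrow below 5% (0 or 1 point), hemoglobin (0, 1 or 1.5), platelets of at least 50 x 10⁹/L under exclusion 9 (0 or 0.5), ANC (0 or 0.5). That gives 2 x 3 x 2 x 2 = 24 combinations per cytogenetic group. The highest non-cytogenetic total is 1 + 1.5 + 0.5 + 0.5 = 3.5. Eligibility needs a total of at most 4.5.

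| Cytogenetics (points) | Maximum score | Combinations at or below 4.5 |
|---|---|---|
| Very good (0) | 3.5 | 24 of 24 |
| Good (1) | 4.5 | 24 of 24 |
| Intermediate (2) | 5.5 | 20 of 24 |
| Poor (3) | 6.5 | 11 of 24 |
| Very poor (4) | 7.5 | 3 of 24 |

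These are cells of a scoring grid, not patient frequencies. They show that the risk limit does not reliably exclude the subject. They do not show how often the subject occurs.

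**3. Exposure before the blast result**

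- Luspatercept: W1D1 may be given with the result pending (Table 5, footnote k), which is 1 dose.
- Epoetin alfa: if the first blast result acted on is the mandatory W4D1 assessment (Table 7, footnote i), the doses are W1D1, W2D1, W3D1 and W4D1, which is 4 doses.
- Footnote k requires the result within 3 days of dosing, so it arrives before the next dose in either arm.

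Both are upper bounds. Table 3 schedules hematology at W1D1, W2D1 and W3D1, and any local or central sample can trigger the rule.

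**4. Effect on power**

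Inputs from Section 9.3: 36% against 20%, 175 per arm, one-sided 0.025, test on the odds ratio.

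- Log odds ratio = ln[(0.36/0.64)/(0.20/0.80)] = 0.811.
- Variance factor = 1/(0.36 x 0.64) + 1/(0.20 x 0.80) = 10.59.
- Standard error = √(10.59/175) = 0.246, so z = 0.811/0.246 = 3.30.
- Power = Φ(3.30 − 1.96) = 90.9%. The plan states 90%, so its figure is reproduced. The matching size for 90% power is about 170 per arm, or 340 in total.

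Now assume that a share f of each arm is affected and that none of them responds, so both rates are multiplied by (1 − f). The documents give no f, and this range is an assumption.

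| f | Subjects of 350 | Response rates | Power |
|---|---|---|---|
| 0 | 0 | 36.0% / 20.0% | 90.9% |
| 0.5% | 1.75 | 35.8% / 19.9% | 90.7% |
| 1% | 3.5 | 35.6% / 19.8% | 90.6% |
| 3% | 10.5 | 34.9% / 19.4% | 89.8% |
| 5% | 17.5 | 34.2% / 19.0% | 88.9% |

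**The case against.** The best defense is the mandatory central review. Section 6.1.1 has marrow and blood read centrally to confirm diagnosis and WHO class before randomization, so blood blasts of 2% or more should be seen and labeled MDS-EB. The investigator could then apply exclusion 22 ("Subject has any condition including the presence of laboratory abnormalities, which places the subject at unacceptable risk") or exclusion 23 ("Subject has any condition or receives concomitant medication that confounds the ability to interpret data from the study") to a known result, and exposure could be zero. This stands as to detection. It does not close the gap: MDS-EB is a valid WHO 2016 MDS diagnosis, no rule excludes it once identified, and exclusions 21 to 23 leave the decision to judgment with no blood-blast limit.

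A second point is that the stop is less automatic than it looks. Footnote g also sets central confirmation of marrow blasts below 5% as a condition for resuming treatment, and this subject may meet it. With footnote h and Section 11.1, withdrawal is directed but reviewable. That is fair. Still, none of these is a written exception for a value present at baseline, how footnote g fits with the confirmed-blast branch is unclear, and footnote k calls for immediate action under the table.

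Third, the stop itself protects anyone who slips through, the subject is probably rare, and power is barely touched. All of this is true. It limits the urgency of the point but does not remove the conflict between the two rules.

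**Conclusion.** The concern holds. Entry has no blood-blast limit, exclusion 2 catches the twice-recorded 1% category, and 2% or more with marrow below 5% is not excluded by name, while the treatment stop sits at 1% with no baseline exception. Confidence in this reading is high because it rests on the text alone.

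The practical size is small. The number affected is unknown and assumed to be low. The power loss is 2.0 percentage points at an assumed 5% affected (90.9 − 88.9) and 0.3 at an assumed 1% (90.9 − 90.6), in both cases assuming no responders among them. The dose bounds assume that the screening smear was not acted on and, for epoetin alfa, that no blast result before W4D1 was acted on. The change should be made for patient safety and agreement between entry and dosing rules; nothing in the sample size needs revisiting.

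**What to change.** Add a second limit to criterion 4 in Section 4.2, beside the marrow one: peripheral-blood blasts below 1%, by central cytomorphology of the screening smear. The central smear should govern over a local or automated differential, as it does in Tables 5 and 7, so that no subject fails on an unconfirmed count. Where rescreening or a central over-read of local samples is used (Section 6.1.1), specify that the smear must come from the current screening window. This excludes EB-1 and EB-2 reached by blood count, aligns entry with the stopping threshold, and covers a single 1% reading, which MDS-U misses because Appendix B asks for two.

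No new test is needed, since the blood smear is already reviewed centrally before randomization (Sections 3.1 and 6.1.1). The change requires an amendment with written IRB/EC approval before use (Section 13.5), so it is best bundled with the next one. It may cause a few more screen failures, and it cannot help subjects already randomized.
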